3.3.3.4 Cessation of Study Medications

If medications are thought to be causing unacceptable symptoms, the treating doctor will determine the likely pharmacological cause (either of the two study drugs, or any of the four TB drugs) according to the strategy outlined in Appendix 5. If symptoms are determined to be due to arginine, this will be immediately ceased, and reintroduced at a lower dose as outlined in Appendix 5. If symptoms are due to vitamin D/hypercalcaemia, appropriate hypercalcaemia management will be instituted and any further scheduled dose of vitamin D will be cancelled. Any such events will be recorded on the 'Adverse drug events' sheet (Appendix 6) and notified immediately to the study investigators.

3.3.4 Participant Evaluations

3.3.4.1 Clinical, Radiological, Physiological and Functional Evaluations

1) Height

Standing height in centimetres will be measured without shoes to the nearest centimetre using a stadiometer, ensuring that the tragus is level with the eyes.

2) Weight

Weight in kilograms will be measured without shoes to the nearest 0.1kg using an adult balance.

3) Body Mass Index (BMI)

BMI will be calculated in the standard way:

 $BMI = \frac{weight(kg)}{height(m)^2}$

4) Questionnaire

A questionnaire to obtain demographic and clinical information will be completed (see TB Baseline Data Collection form, Appendix 1)

5) Chest radiograph

A postero-anterior chest x ray will be performed as per standard clinical protocols at the TB clinic and the RSMM, whether or not the patient is enrolled in the study. Chest Xrays will be evaluated by two study investigators using a previously validated scoring system. The percentage of abnormal lung will be assessed and averaged. The presence or absence of cavitation will also be recorded.

6) Lung Function

Respiratory function will be measured as outlined in Appendix 12 using the hand held spirometer (MicroLoopTM, Micro Medical, UK) used in our previous studies, which will be calibrated daily. Each patient will perform at least three maximum effort expirations until volumes vary less than 200mls, with the highest values for FVC and FEV₁ used as measures of lung function. [name] will supervise the QA/QC of this test.

7) Exhaled nitric oxide

Exhaled NO will be used to measure pulmonary NO production at the TB Puskesmas and RSMM, using the online NIOX Mino[™] (Aerocrine, Sweden), as detailed in Appendix 13.

8) Modified St George Respiratory Questionnaire (MSGRQ)

The SGRQ (see Appendix 17) is a valid self-complete measure of health status for patients with lung disease. An overall score and individual domain scores for symptoms, activity and impacts on daily life, are obtained. Patients will be requested to complete the questionnaire without assistance

where possible in order to obtain objective responses, but with assistance from clinic staff if required.

9) 6 minute walk test (6MWT)

The 6 minute walk test will be performed in keeping with standard ATS guidelines as described in Appendix 13. The six minute weight distance (6MWWD), calculated by multiplying this distance in kilometres by the subject's weight in kilograms, will be calculated.

10) Sputum collection

Sputum collections will be obtained at baseline from each TB patient in accordance with NTP standard protocols (minimum of 2 positive smears) prior to enrolment in the study. An additional sputum specimen will be obtained on the day of entry into the study. The study sputum specimen containers will be distinct from standard sterile specimen jars used at the clinic or hospital, and will be labelled with the patient's details (name, study ID number, age, sex), date of collection and laboratory number. A microscopy slide will be prepared from this specimen and examined using standard Zeihl Neelsen method, labelled using a diamond-tipped pen as above and stored at the NIHRD-MSHR Research Building for later QA. Sputum specimens will be divided to provide material for smear examination, antigen testing, culture, susceptibility testing and MIRU typing as detailed in Appendix 15.

11) Blood collection

Twenty mL venous blood (a safe amount) will be collected from participants at enrolment and at follow up weeks 2, 4, 8 and 24 as described in Appendix 15.

12) Urine Collection

A midstream urine specimen will be collected into a sterile specimen container for TB antigen testing as detailed in Appendix 15.

3.3.5 Follow up

Usual follow-up according to the NTP includes monthly weight, repeat chest x ray and sputum at 2 and 6 months, and recording of symptoms, adherence and side-effects. Study participants in addition will receive evaluations as indicated in the table below. Default tracing will comprise three attempts to trace participants who miss two consecutive scheduled clinic appointments, which is standard practice in Timika.

test		week of TB treatment											
	0	1	2	3	4	5	6	7	8	12	16	20	24
weight (weekly)													
symptoms (weekly)													
sputum microscopy*													
sputum culture													
Chest Xray (routine 0,2,6 mths)													
expired NO													
spirometry													
6 minute walk test													
Respiratory Questionaire (SGRQ)													
blood													
HIV													
25(OH)D3 1,25(OH)2D3 & L-arginine													
iSTAT (including iCa2+, Hb)													
T cell CD3 ζ and function													

Notes:

1. Grey cells indicate that the test will be performed during this week (week 0 = diagnosis, other weeks are follow-up during TB treatment).

2. Routine tests/data collection as part of normal clinical practice in Timika TB clinic/RSMM: weight, symptoms, sputum microscopy (at week 0,8 and 24), chest Xray, HIV

3. Study-related tests/data collection: sputum microscopy (at week 1-7), sputum culture, expired NO, spirometry, 6 minute walk test, respiratory questionnaire and blood tests (vit D, arginine, Ca++ and T-cell function).

3.4 Time line

Table 2: Proposed timeline for ADAPT

Period	Tasks
March 2008-July 09	Recruitment of patients in Timika, lab work commences.
Jul 2009- Oct 2010	Patient follow-up and laboratory work continues.
Oct 2010 – Dec 2010	Completion of laboratory work in Darwin and data analysis
January 2011	Dissemination of results: Timika workshop, report to MoH
	and publications.

4 TRIAL OUTCOME MEASURES

4.1 Primary outcome measures

- 1. Proportion of pulmonary TB patients who are culture negative at 1 month
- 2. Difference in improvement in composite clinical endpoint comprising weight, cough clearance and FEV_1 at 2 months.

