1.1.7 Anticipated Benefits to local medical staff and the wider community

Preliminary discussions regarding TB treatment in Timika, undertaken in planning this study, have revealed that medical staff at RSMM and the TB Clinic have particular concerns about poor adherence to treatment by patients, loss to follow up, HIV-TB co-infection, and the emergence of drug-resistant TB. The structures and resources associated with this proposed study will help to address these concerns: in particular, two dedicated TB Research Assistant positions will be created. Anticipated benefits of the study, building on those listed in 1.1.2, are summarised as follows:

- Support for medical staff in implementing the National TB Protocol (NTP):
 - Two dedicated nurses to work as TB Research Assistants
 - o Access to research vehicle to assist in follow up of treatment defaulters
 - In-services by NTP and Research staff to provide continuing professional development for local medical and nursing staff on the topic of TB, including highlighting HIV testing and treatment in TB
- Quality assurance practices including examination of all sputum smears at the WHO Supranational TB Reference Laboratory
- TB culture and sensitivity testing to be performed at Supranational TB Reference Laboratory as previously (during 2003-4 studies) to:
 - Provide confirmation of TB diagnosis or otherwise (e.g. rates of non-tuberculous mycobacterial pulmonary infections)
 - Complement the national drug resistance survey currently underway in several other sites in Indonesia by providing ongoing information to NTP and WHO on multi-drug resistant TB (MDR-TB) rates
 - o Allow individual patient medication regimens to be tailored if resistant isolate identified
- Measures of Vitamin D status of people with TB and healthy controls will provide important information about vitamin D deficiency rates, recognised globally as an emerging health problem
- Potential benefits related to study intervention: if L-arginine and / or vitamin D are found to be beneficial as we and other researchers propose, this will have major positive impacts on TB outcomes for patients enrolled in the study who receive active intervention. If shown to be beneficial, wider roll-out of these treatments can then be undertaken.

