3.2.1 Inclusion criteria

Adults 15 years of age or older will be recruited if they have sputum smear positive pulmonary TB; have never received more that one month of anti-TB treatment in the past (that is, only new cases of TB will be included); agree to continue treatment in Timika for the full six month course of treatment; are not pregnant, and consent to enrol in the study.

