5.2 Outcome Analysis

The primary analysis of all outcomes will be by intention to treat. All participants in the study will contribute outcomes for analysis whenever possible. Each participant's success or failure for the primary outcome will be determined by an independent observer who will be blinded to the intervention. Analyses will use Intercooled Stata 9.2 (Stata Corp, College Station, Texas, USA). 95% confidence intervals and/or p values <0.05 will be employed to signify statistical significance.

As per recent clinical journal requirements, ADAPT will be registered with the protocol registration system at Clinicaltrials.gov.

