Appendix 14: Sputum Specimen Handling and Processing

TEST	VOLUME REQUIRED	LOCATION OF TESTING	METHOD
Sputum			
Microscopy	1 mL	RSMM &/or TB Clinic, Timika QA at WHO Reference Laboratory, Adelaide	Ziehl Nielsen stain
Proteome Systems' rapid diagnostic (RD) test	3 mL	RSMM &/or TB Clinic, Timika,	Antigen detection kit
QA Culture, Drug Sensitivity, Molecular typing	8 mL	WHO Supranational Reference laboratory, Adelaide	Mycobacterium Growth Indicator Tube (MGIT), Standard methods (see below). MIRU typing.

Table 6: Summary of Sputum testing to be performed for ADAPT

Sputum Collection and Handling

After collection in sterile specimen containers, sputum specimens will be kept in a domestic refrigerator at +4°C in the TB clinic or RSMM until ready for batched transport by air with a commercial courier via Darwin to the WHO Supranational Reference laboratory at the Institute of Medical and Veterinary Sciences (IMVS) in Adelaide, Australia. Preparation and packaging of the specimens will comply with International Air Transport Association (IATA) regulations. Specimens will not be decontaminated prior to storage, and will be sent at three to six week intervals during the study period. After leaving the TB clinic or RSMM Laboratory, specimens will be kept at room temperature until arrival at the reference laboratory. We have previously demonstrated success in culturing MTB in over 94% of smear positive sputum samples, despite considerable delays in transport to the Adelaide laboratory (mean 18.7, range 4-42 days).(89)

Location of testing

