Wherever possible, specimens will be processed locally. Thus sputum microscopy and the novel antigen testing will be performed in Timika. There is no capacity for TB culture in Timika. It is our understanding that the nationally accredited TB culture laboratories in Indonesia (in Surabaya and Jakarta) are operating at maximum capacity and are fully committed to work related to the ongoing National TB drug resistance survey. Furthermore, it is mandatory for TB research to demonstrate participation in a quality assurance program. We therefore propose that sputum culture, sensitivity and typing should be performed at the WHO Supranational Reference Centre (IMVS, Adelaide) with whom the National TB Control Program is currently collaborating with a range of training, guideline development and quality assurance activities. Our previous experience of transferring samples from Timika to the WHO reference Laboratory has been successful. Additionally, processing at the WHO reference Laboratory will provide excellent training opportunities for NIHRD laboratory scientist ([name]) to work on Indonesian samples in a supportive environment with world class training.

Methods

• Ziehl Nielsen (ZN) staining and light microscopy

ZN staining is performed routinely at Timika Puskasmas and RSMM laboratories in accordance with NTP guidelines.

• Proteome Systems' rapid diagnostic (RD) test

3 mL sputum will be reserved for antigen testing. Protease will be added and the sample will be frozen for subsequent batched antigen testing using Proteome Systems' rapid diagnostic (RD) testTM at RSMM laboratory.

• Culture

Upon arrival at IMVS, Sputum specimens will be decontaminated using 2% sodium hydroxide and 0.5% N-acetyl-cysteine for 25 min, then neutralised to pH 7, concentrated by centrifugation (3,000xg for 15 min) and inoculated into a single Mycobacterium Growth Indicator Tube 960 (MGIT; Becton Dickinson Microbiology Systems, Sparks, Md). Microscopy of sputum concentrates will be performed using fluorochrome and ZN stains and results recorded using standard IUATLD grading scales. Contaminated specimens will be re-decontaminated with 4% sulphuric acid.

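### Primary outcome 1 scores culture negativity at 1 month without requiring a positive pre-treatment culture, and the longest shipping interval goes beyond the delays on which its culture-recovery figure rests

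*Protocol*

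**What the plan says.** Protocol section 4.1 defines the first primary outcome as "Proportion of pulmonary TB patients who are culture negative at 1 month". Section 3.2.1 sets entry by smear: "Adults 15 years of age or older will be recruited if they have sputum smear positive pulmonary TB". Section 5.2 makes intention to treat the primary analysis and adds that "All participants in the study will contribute outcomes for analysis whenever possible". It also says that "Each participant's success or failure for the primary outcome will be determined by an independent observer who will be blinded to the intervention".

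A sputum specimen for culture is taken on the day of entry (section 3.3.4.1, item 10; week 0 in the Appendix 2 testing table). Neither section 4.1 nor section 5.2 links its result to the outcome. Section 1.1.7 lists this among the uses of culture: "Provide confirmation of TB diagnosis or otherwise (e.g. rates of non-tuberculous mycobacterial pulmonary infections".

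On handling, Appendix 14 keeps sputum at +4°C on site and then says "Specimens will not be decontaminated prior to storage, and will be sent at three to six week intervals during the study period". After leaving the site, specimens stay at room temperature until they reach Adelaide, where each is "inoculated into a single Mycobacterium Growth Indicator Tube 960". The support offered is this: "We have previously demonstrated success in culturing MTB in over 94% of smear positive sputum samples", with transport delays averaging 18.7 days and ranging from 4 to 42.

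Section 5.1 plans on culture positivity falling from 60% to 40% at one month. It states 82% power with 444 participants (111 per arm), 10% loss, a 5% significance level and an interaction coefficient of 0.5.

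**The concern.** The outcome measures negativity, not conversion. A patient whose pre-treatment specimen grows nothing, and whose week-4 specimen also grows nothing, is a success although no change could be seen. The protocol allows for such patients. Its recovery figure is below 100%. It foresees that culture may not confirm TB. It admits people with up to one month of past treatment (section 3.2.1), and section 4.2 recognises that smears can stay positive from non-viable organisms. Such patients fall in every arm and shrink the absolute difference between arms.

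The second issue is viability. Section 4.2 justifies culture because it avoids counting dead organisms, so the endpoint depends on live bacilli surviving storage. The recovery evidence comes from smear-positive sputum held for at most 42 days. Week-4 sputum from treated patients can carry far fewer bacilli, and the shipping plan allows longer delays.

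**Working it through.** **Inputs from the protocol.** 60% v 40% culture positive, 111 per arm, 10% loss, 5% significance (section 5.1; two-sided is assumed, as sidedness is not stated). Recovery over 94%, delays of 4 to 42 days, shipping every three to six weeks (Appendix 14).

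**1. The stated power.** Evaluable patients per arm: 111 × 0.9 = 99.9, about 100. With the unpooled normal approximation,

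power = Φ( |p1 − p2| / √[(p1(1−p1) + p2(1−p2))/n] − 1.96 ).

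For 60% v 40% and n = 100: 0.20 / √(0.48/100) = 2.887; 2.887 − 1.96 = 0.927; Φ = 82.3%. The Fleiss pooled-variance form with 99.9 per arm gives 81.2%. For the factorial margin, take the interaction as half the effect on the risk-difference scale. The four cells are then 60, 40, 40 and 30%, so the margins are 50% v 35% with 199.8 each, and power is 83.7% with continuity correction. The stated 82% is reproduced to within two points.

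**2. Patients who cannot show a positive culture.** Let f be their share, equal in all arms. Observed positivity is p × (1 − f). The protocol gives only a ceiling, f ≤ 1 − 0.94 = 0.06:

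- control: 0.60 × 0.94 = 56.4%
- active: 0.40 × 0.94 = 37.6%
- difference: 18.8 points instead of 20
- risk ratio: 37.6/56.4 = 0.667, the same as 40/60

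Unpooled power, n = 100: 0.188 / √[(0.564 × 0.436 + 0.376 × 0.624)/100] = 0.188/0.0693 = 2.712; 2.712 − 1.96 = 0.752; Φ = 77.4%.

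**3. Restricting to patients with a positive pre-treatment culture.** The 60% v 40% returns, with n × 0.94 patients. Unpooled, 94 v 94: 0.20 / √(0.48/94) = 2.799; 2.799 − 1.96 = 0.839; Φ = 79.9%.

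| Method | No loss | 6% kept as negatives | 6% excluded |
|---|---|---|---|
| Unpooled, 100 per arm | 82.3% | 77.4% | 79.9% |
| Fleiss pooled, 99.9 per arm | 81.2% | 76.3% | 78.7% |
| Factorial margin 50% v 35%, continuity-corrected, 199.8 per margin | 83.7% | 79.5% | 81.2% |

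The loss at the ceiling is 4 to 5 points, and restriction recovers about 2 to 2.5. At an assumed f of 3%, the pooled single-arm figure is 78.8% with everyone kept and 80.0% after restriction.

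**4. Storage time.** With a six-week interval, the oldest specimen is 6 × 7 = 42 days old when it leaves Timika, so any transit time takes it past the 4 to 42 day range. With a three-week interval, the oldest leaves at 21 days and stays within 42 if transit takes no more than 42 − 21 = 21 days. The protocol does not state transit time.

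**5. Direction of storage loss at week 4.** If loss is equal in both arms, the risk difference shrinks. If it rises as bacillary load falls, an effective arm loses more. With assumed loss of 6% in control and 12% to 20% in active, positivity is 56.4% v 35.2% to 32.0%, a difference of 21.2 to 24.4 points. That exaggerates the effect.

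**The case against.** The strongest reply is that section 4.1 is one line, and analysis sets are commonly left to an SAP, which is not at hand. The denominator is pulmonary TB patients, and culture is meant to confirm that diagnosis, so a confirmed-TB set is not excluded. This tempers the point. Even so, section 4.1 fixes the outcome, section 5.2 fixes the population, and neither uses the pre-treatment culture.

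The 6% is recovery per specimen. A patient whose first specimen was lost to delay may still grow at week 4. That stands, so 6% is a ceiling and not an estimate. The planned 60% might also already mean observed positivity, in which case the multiplication counts the loss twice. Section 5.1 derives it from bacillary burden and cavitation and does not mention stored specimens, but it does not settle the matter.

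On storage, specimens are refrigerated until shipment. With steady accrual the average hold is half the interval, 10.5 to 21 days, against the 18.7-day mean delay in the evidence. Most specimens should therefore fall within the supported range, and the point concerns the oldest in each batch and low-load sputum.

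Restriction departs from the stated intention-to-treat set. However, section 3.3.2 places the baseline evaluations before the first dose, so the restriction rests on pre-treatment status and does not bias the randomised comparison.

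**Conclusion.** The point holds in a limited form. Followed as written, the outcome counts patients who never grew M. tuberculosis as successes in every arm. The cost is at most about 5 points of power (82.3% to 77.4%). This assumes the 6% ceiling, equal shares across arms, and a planned 60% that does not already include imperfect recovery. Separately, the six-week shipping interval exceeds the protocol's own evidence, with a consequence of unknown size and direction.

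A reader might go further in four ways that the protocol does not support:

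- Much lower power can be computed by assuming poorer week-4 recovery, but the protocol gives no such figure.
- Storage loss need not dilute both drug effects; step 5 shows it could exaggerate one.
- A null result would not be wholly indistinguishable from failed growth. Baseline cultures travel the same route, so a handling failure would show at least partly in baseline recovery and in control-arm positivity.
- Nothing says that contaminated cultures are scored negative. Appendix 14 has them decontaminated again.

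**What to change.** **Outcome.** Make the main analysis of primary outcome 1 the randomised patients whose pre-treatment specimen grew M. tuberculosis, and report all randomised patients as a sensitivity analysis. The endpoint then means conversion. The cost is a change of wording and up to about 6% of patients in that analysis: 444 × 0.9 × 0.06, about 24 of 400 evaluable. The result then applies to culture-confirmed disease.

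**Specimens.** Ship week-4 specimens towards the protocol's own three-week interval, so that collection-to-inoculation time stays within 42 days where transit allows. Record that time for each specimen, and repeat the primary comparison adjusted for it as a sensitivity analysis. The cost is some extra courier shipments and one data field. No new test, staff or patients are needed.

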4.2 Secondary outcome measures

- 1. Safety.
- 2. Difference in improvement in percent predicted FEV_1 at 2 and 6 months.
- 3. Change in plasma L-arginine and 25(OH)D₃ concentrations.
- 4. Weight gain.
- 5. Cough clearance.

- 6. Sputum smear conversion time.
- 7. Functional improvement including Six minute walk test and quality of life assessment using modified St George Respiratory Questionnaire.
- 8. Immunological improvement (exhaled NO, T cell CD3ζ expression and T cell function).
- 9. Radiological improvement (percentage lung involvement on CXR at 2 months).
- 10. Percentage obstructive and/or restrictive lung disease at 6 months.
- 11. Death, clinical failure and default independently, and 'death or clinical failure or default'.
- 12. Primary end points stratified by HIV status.
- 13. Primary end points stratified by baseline vitamin D and L-arginine status.
- 14. Primary end points stratified by ethnicity (Papuan and non-Papuan patients).

Use of mycobacterial culture as a primary outcome measure overcomes the potential problem of continued smear positivity of non-viable organisms. Culture at one month will capture any early microbiological effect of adjuvant therapy. As we have shown in previous work in Timika, FEV_1 at 2 months is predictive of longer term deficits in lung function that may be modified by early adjuvant therapy. We will also determine the relationship between baseline and serial measurements of pulmonary NO production, serum L-arginine and 25(OH)D₃ concentrations, and clinical, radiological, microbiological and functional measures of disease severity.

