5 STATISTICAL ANALYSES

5.1 Sample size

Sample size has been calculated using the graphical method for 2x2 factorial designs informed by the Fleiss equation, described by Byth and Gebski (71). Making a conservative assumption of sub-additive interaction between the 2 interventions (interaction coefficient of 0.5), then at a level of significance of 5%, a sample size of 444 (111 participants in each arm) will provide 82% power to demonstrate that each treatment results in a 20% reduction in the proportion culture positive at one month (from 60% to 40%), assuming loss to follow up of 10%. As there have been no trials of co-administration of vitamin D and L-arginine, the characteristics of potential immunological interactions can be extrapolated only from in vitro macrophage studies, in which findings conflict: vitamin D was found to inhibit iNOS expression in one study(44); yet upregulate NOS2A in another (68); the latter study also found the suppressive effect of vitamin D on MTB replication to be partially impaired if NO formation was inhibited. Including a sub-additive interaction term in the sample size calculation provides a margin a caution; if there is minimal or no interaction between the two interventions, our power will be greater. A factorial design rather than a three-arm study allows us to investigate whether if is safe and effective to co-administer the two interventions. Acknowledging the possibility of statistical interaction between the terms, we have an *a priori* plan to analyse primary and secondary outcomes according to subgroups receiving single interventions as well as according to the overall factorial model (71).

Mean time to culture negativity in mostly drug sensitive TB is 32 days (New York) (72) -57 days (Turkey) (73). Based on bacillary burden and extent of cavitatory disease, we estimate a minimum of 60% of Timika patients will be culture positive at 1 month. Our power will be increased if this proportion is higher. This sample size will also be powered to detect a 9% absolute difference in the mean improvement in percent predicted FEV1, a component of the composite endpoint, at 6 months. Mean baseline percent predicted FEV1 in Timika is 63.6% predicted (SD 22) rising to 77.9% predicted (SD 23) at 6 months. Each month, at least 25 eligible smear positive pulmonary TB patients are diagnosed and treated at the Timika study site. If 90% agree to be enrolled, recruitment will take <2yrs to complete.

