7 RANDOMISATION AND BLINDING

A random allocation sequence will be computer-generated (Intercooled Stata 9.2) and concealed from all investigators throughout the study. The random assignment to intervention group will be provided by the MSHR statistician. Block randomisation will be used to maintain similar numbers of participants in the intervention and control groups and to minimise the potential influence of time of enrolment. Allocation will be stratified by place of TB diagnosis (hospital or clinic) and ethnicity (Papuan/non-Papuan), the latter because of the different Vitamin D status of these two groups (as per preliminary data). Allocation concealment will conform to the revised CONSORT guidelines which take account of the logistically challenging environment at the study site (82). We have successfully used this method in over 1,200 malaria patients (three RCTs) in Timika (1, 2, 4). The random allocation will be in sealed, opaque envelopes in two boxes (Papuan and non-Papuan) in each study location. Prior to opening the envelope, the investigator will complete the randomisation form to check if the patient is eligible for enrolment, obtain informed consent and complete the enrolment questionnaire.

Placebo will be compounded to be indistinguishable by appearance, smell and taste from the matching active medication. All study personnel and participants will be blinded to treatment assignment for the duration of the study. Only the study statistician and the Data Safety Monitoring Committee will see any unblinded data and these individuals will not have contact with study participants. The randomisation code will be kept at MSHR by an independent person unrelated to the study. The randomisation sequence will not be broken until primary outcomes have been measured and agreed by the study investigators.

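### The 9-point FEV1 claim depends on an unstated baseline correlation if improvement is compared as a plain change score; adjusting for baseline FEV1 removes that dependence at no cost

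*Protocol*

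**What the plan says.** Protocol section 4.2, item 2, gives the lung-function outcome as "Difference in improvement in percent predicted" FEV1 at 2 and 6 months. Section 4.1 words the second primary outcome in the same way: "Difference in improvement in composite clinical endpoint comprising weight, cough clearance and" FEV1 at 2 months.

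Section 5.1 says the sample size is also powered to detect a "9% absolute difference in the mean improvement in percent predicted FEV1" at 6 months. The supporting figures are a mean of "63.6% predicted (SD 22) rising to 77.9% predicted (SD 23) at 6 months". No correlation between the two measurements, no SD of the change and no power for this particular claim are given. The same section commits to analysing outcomes in the single-intervention groups as well as in the overall factorial model.

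Section 7 states: "Allocation will be stratified by place of TB diagnosis (hospital or clinic) and ethnicity (Papuan/non-Papuan"). Section 5.2 states: "The primary analysis of all outcomes will be by intention to treat". Neither 5.1 nor 5.2 names a covariate or rules one out.

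**The concern.** The most direct reading of a difference in mean improvement is to subtract baseline from follow-up and compare the arm means. The variance of that difference depends on how strongly baseline and 6-month FEV1 are correlated. With a weak correlation, subtracting baseline adds noise, and the change score can be less precise than the 6-month value alone. The two SDs in section 5.1 do not fix the correlation, so a reader cannot tell whether the 9-point claim holds for a change-score comparison.

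At stake is power for FEV1 in the smaller comparisons of one active arm against placebo. A baseline-adjusted comparison uses the same data, is never less precise, and does not need a favourable correlation.

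**Working it through.** **Inputs.** From section 5.1: SD 22 at baseline and 23 at 6 months, target difference 9 points, significance level 5% (two-sided assumed, as the side is not stated), 111 per arm, 10% loss. Evaluable per arm: 111 × 0.9 = 99.9, taken as 100; each factorial margin is then 200 v 200. The correlation r is not in the protocol, so a range is assumed.

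**Formulas.**
- Change-score variance: 22² + 23² − 2r(22)(23) = 1013 − 1012r.
- Baseline-adjusted (ANCOVA) residual variance: 23²(1 − r²) = 529(1 − r²).
- Power: Φ(9 / (SD × √(2/n)) − 1.96).

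**The protocol's own figure.** With 100 per arm, 9 points gives 82.5% power at SD 22, 80.7% at SD 22.5 and 79.0% at SD 23. The claim therefore reproduces at about 80% power. An SD of 22.5 is the change-score SD at r = 0.5 (√507 = 22.5), but the raw SDs of 22 and 23 fit equally well, so the text does not show which basis was used.

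**Comparison at 100 v 100, 9 points.**

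| r (assumed) | Change SD | Adjusted SD | Variance reduction | Power, change | Power, adjusted | n per arm for 80%, change → adjusted |
|---|---|---|---|---|---|---|
| 0.3 | √709.4 = 26.6 | √481.4 = 21.9 | 32% | 66.6% | 82.7% | 138 → 94 |
| 0.5 | √507.0 = 22.5 | √396.8 = 19.9 | 22% | 80.7% | 89.2% | 99 → 77 |
| 0.7 | √304.6 = 17.5 | √269.8 = 16.4 | 11% | 95.4% | 97.2% | 60 → 53 |
| 0.8 | √203.4 = 14.3 | √190.4 = 13.8 | 6% | 99.4% | 99.6% | 40 → 37 |

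At r = 0.9 the variance reduction is 2%.

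**Bounds.** The change-score SD exceeds 23 when 1013 − 1012r > 529, that is, when r < 484/1012 ≈ 0.48. The adjusted SD is 23√(1 − r²), which cannot exceed 23, so adjusted power does not fall below about 79.0%. The gap between the two variances is (22 − 23r)². It is never negative and is zero only at r = 22/23 ≈ 0.96.

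**Detectable difference at 80% power, r = 0.5.** From (1.96 + 0.84) × SD × √(2/n): 8.9 v 7.9 points at 100 per arm, and 6.3 v 5.6 points at 200 v 200.

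**Factorial margin, 200 v 200, r = 0.5.** Power is 97.9% for the change score and 99.5% adjusted.

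**Same estimate either way.** If follow-up is modelled as a + b·treatment + c·baseline, then change equals a + b·treatment + (c − 1)·baseline. The treatment coefficient b and its standard error are identical, so the outcome can still be reported as improvement.

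**The case against.** The strongest reply is that covariates are normally set in the statistical analysis plan, which is not shown, and that defining an outcome as improvement does not prescribe an unadjusted test. Both points are right. Regressing change on treatment and baseline satisfies the wording of sections 4.1 and 4.2, so nothing in the protocol blocks the better analysis. What stands is narrower: section 5.1 makes a quantitative claim about mean improvement without the quantity that a plain change-score comparison would need, and one sentence makes the claim safe.

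A reader might infer that the trial stratifies its randomisation and then ignores the strata. The documents do not support that. Silence in 5.2 is not a decision, and section 4.2, item 14, presents the primary end points by ethnicity. That presentation differs from adjusting the main comparison, and place of diagnosis appears in no analysis statement, but neither fact shows that the strata will be left out.

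It can also be said that the loss matters only at low r. That is correct: at r = 0.5 the change score already detects 8.9 points with 100 per arm, and at r = 0.7 its power is 95%.

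**Conclusion.** The point holds as a minor, cost-free improvement. As a plain change score, the 9-point FEV1 claim at 100 per arm has power from about 67% (r = 0.3) through 81% (r = 0.5) to 95% (r = 0.7). With baseline adjustment these become about 83%, 89% and 97%, with a floor of about 79%. This rests on the SDs in section 5.1, a two-sided 5% test, 100 evaluable per arm and an assumed r. The benefit is real for the single-intervention comparisons at low to moderate r, small on the factorial margin at r = 0.5, and negligible at r of 0.8 or above.

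Three stronger readings are not supported. First, no bias or inflated type I error follows: an unadjusted change score remains valid in a randomised comparison. Second, the stated sample size is not shown to be wrong, since the 9-point figure reproduces at about 80% power. Third, no size can be put on a gain for culture, weight or the composite. The protocol gives no stratum-specific culture rates, no SD or correlation for weight, and no scoring of the composite to which the change-score formula could be applied.

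**What to change.** Add to section 5.2 that FEV1 and other continuous outcomes reported as improvement are compared by linear regression on both treatment factors, with the baseline value, place of diagnosis and ethnicity as covariates. Use the same covariates in the single-intervention comparisons. The results may still be presented as change from baseline.

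Optionally, include the two randomisation strata in the main comparison of culture status at 1 month, in addition to the presentation by ethnicity in section 4.2, item 14. The documents allow no figure for that gain.

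In section 5.1, either state the correlation assumed for the 9-point claim or say that the claim refers to the baseline-adjusted comparison.

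The cost is wording only. Spirometry is already done at week 0, and enrolment site and ethnicity are already recorded on the baseline form (Appendices 1 and 2). No new data, visits or participants are needed.
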